9. STATISTICAL CONSIDERATIONS

Primary/Secondary Objectives:

This is a randomized, open-label, Phase II, for HR positive advanced breast cancer patients who have been treated with AI and CDK as first line in the metastatic setting for at least 12 months and who have *ESR1* mutations identified through ctDNA assay.

[name], MS, Department of Biostatistics at MD Anderson Cancer Center, will oversee the implementation of the statistical analysis. The primary endpoint is PFS, which is measured from the date of study randomization to the date of event (ie, death and/or disease progression) or the date of last follow-up if no event has occurred. Survival curves for PFS will be analyzed using the Kaplan-Meier method and survival difference across groups will be examined by log rank test. Patients alive and disease-free at the latest clinical evaluation will be censored for PFS at the date of that evaluation. We will estimate the treatment comparison with 95% confidence intervals and p-value using Cox proportional hazards regression and we will assess the proportional hazard assumption using graphs of rescaled Schoenfeld residuals and related tests. We would attempt to identify independent predictors of PFS using multivariable Cox PH regression analysis. Analysis for OS and PFS from the start of next line of therapy will be performed as described for PFS from the date of randomization. Randomization will be performed using Core. Stratification factors include recurrence free interval (\leq 3 years vs. $>$ 3 years), prior adjuvant endocrine therapy (tamoxifen vs. aromatase inhibitor), and site of metastasis (bone vs. visceral).

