To detect a change in median PFS from 5 months (for AI arm) to 9 months (with fulvestrant arm) would require about 124 patients (assuming 4-5 patients per month accrual, 5 months post-accrual follow-up, 5% two-sided alpha, 80% power, log rank testing). 84 PFS events are expected under the alternative hypothesis. Interim analysis will be performed when 42 PFS events are observed. Using O'Brien-Fleming stopping boundaries, we will stop for futility if the log rank test p-value $>$ 0.72 and stop for success if it is $<$ 0.004. Descriptive statistics and graphical analysis will be used to summarize patients' demographic and clinico-pathological characteristics, and efficacy outcomes. We will use mean (standard deviation) or median (range) to summarize continuous variables and frequency (percentages) for categorical variables. Graphical analysis, such as scatter plots with Lowess smoothers, will be used to assess the correlative structure of outcomes and compare MAF between fulvestrant and AI treated groups. The Pearson correlation, or its non-parametric analogue, the Spearman correlation, will be used to estimate the linear correlation among variables. Radiographic response rate (partial response + complete clinical response) will be estimated and reported with a 95% CI.

Control	Experimental	
Median	Median	Power
5	6	15%
5	7	38%
5	8	63%
5	9	81%
5	10	91%
5	11	96%
5	12	98%

REFERENCES:

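### Randomisation is stratified on three factors that the primary PFS test and hazard ratio are not described as using: the plan is valid, but main-effects adjustment would protect power if the factors are clearly prognostic

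*Combined protocol and SAP*

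**What the plan says.** All of this is in section 9 (Statistical Considerations).

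- **Test.** For PFS, "survival difference across groups will be examined by log rank test". No strata are mentioned.
- **Estimate.** "We will estimate the treatment comparison with 95% confidence intervals and p-value using Cox proportional hazards regression". No covariates are named.
- **Multivariable model.** "We would attempt to identify independent predictors of PFS using multivariable Cox PH regression analysis". This is a search for predictors. Its covariates are not listed, and it is not tied to the treatment comparison.
- **Randomisation.** "Randomization will be performed using Core", with no algorithm given. The factors are said to include recurrence free interval (up to 3 years or longer) and "prior adjuvant endocrine therapy (tamoxifen vs. aromatase inhibitor), and site of metastasis (bone vs. visceral").
- **Sizing and interim.** The trial is sized on "5% two-sided alpha, 80% power, log rank testing". At 42 events, "we will stop for futility if the log rank test p-value" exceeds 0.72, and for success if it is below 0.004.
- **Other endpoints.** "Analysis for OS and PFS from the start of next line of therapy will be performed as described for PFS".

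**The concern.** Stratified allocation balances the arms on the three factors. If those factors predict PFS, the treatment difference varies less from trial to trial than the plain log-rank variance assumes. The test then runs below its nominal 5% and loses power. The unadjusted HR also sits nearer 1 than the HR among patients with the same factor values. The plan has 80% power in the text and 81% in its table, so there is little to spare. The same choice passes to OS and to PFS on next-line therapy.

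A smaller matter belongs to the same edit. Sections 3.1 and 3.2 require neither earlier-stage disease, nor adjuvant endocrine therapy, nor a particular metastatic site. Some eligible patients therefore fit no printed level: metastatic at diagnosis, no adjuvant endocrine therapy, or neither bone nor visceral disease. Others fit two: both adjuvant therapies, or bone plus visceral disease. An adjusted analysis needs one covariate value per patient.

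**Working it through.** **1. Reproduce the plan's figure.** Inputs from section 9: 124 patients, medians 5 and 9 months, 4–5 patients per month, 5 months of further follow-up, 5% two-sided. Assumed: 1:1 allocation, exponential PFS, no dropout, 4.5 per month (accrual A = 124/4.5 = 27.6 months).

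Event probability per arm, with λ = ln 2/median and F = 5: 1 − [exp(−λF) − exp(−λ(A+F))]/(λA).
- AI arm: 0.872 × 62 = 54.1 events.
- Fulvestrant arm: 0.718 × 62 = 44.5 events.
- Total: 98.6 events.

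Freedman power, with h = 5/9: Φ(√98.6 × (1−h)/(1+h) − 1.96) = Φ(9.93 × 0.2857 − 1.96) = Φ(0.877) = 81.0%. This matches the printed 81%, so the stated power is that of a plain log-rank test in a population without prognostic strata.

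**2. Let the factors matter.** Simulation: 124 patients, 27.6 + 5 months, three two-level factors split 50/50 (8 cells), permuted blocks of 4 within cells (assumed), treatment HR 5/9 within every cell, no interim. The baseline hazard is scaled so that the overall medians stay at 5 and 9; the null has both medians at 5. There were 40,000 null and 40,000 alternative runs per row. The factor HR is an assumption and applies to each of the three factors. The adjusted test is the Cox score test with main effects. Figures are percentages.

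| Factor HR | Power at 1.96: plain | Power at 1.96: adjusted | Type I error: plain / adjusted | Power at true 5%: plain | Power at true 5%: adjusted |
|---|---|---|---|---|---|
| 1 | 82.5 | 82.9 | 5.2 / 5.6 | 82.1 | 81.5 |
| 1.25 | 81.2 | 83.1 | 4.8 / 5.6 | 81.6 | 81.9 |
| 1.5 | 77.3 | 82.2 | 4.0 / 5.6 | 79.9 | 80.8 |
| 2 | 67.6 | 80.6 | 3.1 / 5.9 | 74.7 | 78.4 |

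Smaller repeat simulations with separate code agree within about 2 points. For example, at factor HR 1.5 they gave 77.6 vs 81.8 and 78.4 vs 83.5; at factor HR 2, 68.6 vs 81.3 and 69.1 vs 81.5.

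**3. Split the gap at 1.96.**
- Factor HR 1.5: 82.2 − 77.3 = 4.9 points, of which 2.6 is the plain test's unused alpha, 0.9 is adjustment itself and 1.4 is inflation of the adjusted test.
- Factor HR 2: 80.6 − 67.6 = 13.0 points, split 7.1, 3.7 and 2.2 in the same order.

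**4. Only one factor prognostic (site of metastasis).**
- HR 1.5: 81.0 vs 82.9 at 1.96; 81.5 vs 81.3 at a true 5%.
- HR 2: 76.9 vs 81.9 at 1.96; 78.8 vs 80.2 at a true 5%.

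**5. Add the interim stops** (both rules at 42 events, final critical value 1.967; 4,000 runs). For factor HR 1/1.25/1.5/2, plain 80.6/78.5/75.0/65.2 and adjusted 80.7/80.3/80.5/78.9. Both fall by about 2 points, and the gap is essentially unchanged.

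**6. Robustness, plain vs adjusted at 1.96.**
- Minimisation instead of blocks: 77.4 vs 82.4 (HR 1.5) and 67.4 vs 80.7 (HR 2).
- 30% or 70% of patients in the adverse level: 78.0 vs 82.1 and 78.1 vs 82.6 (HR 1.5); 70.6 vs 81.2 and 70.1 vs 81.8 (HR 2).
- Levels completed to 14 feasible cells: 77.6 vs 82.6 (HR 1.5) and 68.1 vs 81.3 (HR 2).

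**7. Estimates.** The within-cell HR is 0.556. The median estimate is 0.55/0.56/0.58/0.61 unadjusted and 0.55 throughout adjusted.

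**8. Stratifying the log-rank on every cell instead.** At factor HR 1 this gives 78.1% with 8 cells and 74.7% with 14, below the plain test. With 8 cells it is below main-effects adjustment at every factor HR tried.

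**9. Null crossing of p < 0.004 at 42 events.** Plain 0.18–0.42%; adjusted 0.59–0.67% (printed levels) and 0.75–0.86% (completed levels).

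**The case against.** The case for leaving the plan alone is substantial.

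- **It is a legitimate choice.** A plain log-rank in a 124-patient Phase II trial is valid, and the sizing, power table and interim rules all use it. This stands, and it limits the point to a suggestion.
- **The gain rests on assumptions.** The documents give no prognostic strength, factor distribution or allocation algorithm. HR 2 on all three factors means a 2 × 2 × 2 = 8-fold hazard range between best and worst cells. This stands. At a true 5% the gain is near zero for weak factors and slightly negative for none.
- **The adjusted test is not free.** With the normal approximation it runs at about 5–6% rather than at or below about 5%. It also crosses the interim success limit about 1.5 to 2 times as often as the nominal rate. This stands and must be dealt with in the fix.
- **The target changes.** The plan defines its effect by overall medians, whereas an adjusted HR is conditional on the factors. This stands, so the unadjusted HR should still be reported.
- **The levels may be complete elsewhere.** The plan says the factors include those listed, so a fuller rule may sit in the randomisation system. The coding rule is therefore a matter of writing it down.

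None of this removes the asymmetry. Recovering the plain test's unused alpha is a real gain for the sponsor, and adjustment costs little if the factors prove weak.

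**Conclusion.** This is worth considering as a low-cost efficiency improvement. It is not an error in the plan. If the factors are clearly prognostic, the plain test is conservative (type I error about 4% at HR 1.5 per factor and 3% at HR 2). Its power is then about 77–78% and 68–69%, against about 81–83% adjusted, before the roughly 2 points that the interim costs both tests. With HR 1.25 or less on each factor, or site alone at 1.5, the plain test keeps about 80–82% and the gain is 0–2 points. At a true 5%, adjustment itself adds about −1 to 0 points at HR 1–1.25, about 1 at 1.5 and 3–4 at 2. These figures assume exponential PFS, 1:1 allocation, no dropout and the factor HRs shown.

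A reader might infer more than the documents support:

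- **That leaving the factors out invalidates the test.** It does not: type I error stays at or below about 5%.
- **That power drops below 80% whenever the factors are prognostic.** It is 81.2% with all three at HR 1.25 and 81.0% with site alone at 1.5, interim ignored.
- **That adjustment is worth 13 points.** That figure needs HR 2 on all three factors, and most of it is unused alpha plus inflation.
- **That this explains low power at the stated 84 events.** The plain test has 75.7% there with no prognostic factors at all, which is a separate matter.
- **That the printed levels show patients cannot be allocated.** The share affected is not given, and a fuller rule may exist.

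**What to change.** In section 9:

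1. Pre-specify the primary PFS comparison, and the HR with 95% CI, from a Cox model adjusted for the three randomisation factors as main effects, not stratified on every cell. State that this HR is conditional on the factors.
2. Report the unadjusted log-rank and the unadjusted HR alongside as sensitivity analyses.
3. State that the interim p-value, for both success and futility, comes from the same statistic.
4. Confirm the type I error of the final and interim thresholds for that statistic, by simulation or by a re-randomisation test that follows the allocation algorithm actually used. With blocks of 4 and the printed levels, a re-randomisation test held the adjusted statistic at 4.8–5.1%, with power of 80.4% (HR 1.5) and 79.7% (HR 2).
5. Write one covariate coding rule for patients who fit no printed level or two, matching any fuller rule already in the randomisation system. It should cover disease metastatic at diagnosis, no or both adjuvant therapies, and bone plus visceral disease or neither. If patients are already randomised, leave the lists alone and use the rule only for coding.

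**Cost.** Text, a coding rule and a short simulation. No extra patients or assessments are needed, since section 6.1 already requires baseline imaging. If no factor is prognostic, about 1–2 points of power are lost at a true 5%. If step 4 is skipped, expect type I error of about 5–6% at the final analysis and about 0.6–0.9%, against 0.4%, for the interim success limit.

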5. TREATMENT PLAN

5.1. Treatment

- **Fulvestrant** 500 mg should be administered intramuscularly (+/- 3 days) into the buttocks slowly (1 - 2 minutes per injection) as two 5 mL injections, one in each buttock, on days 1, 15 of Cycle 1 and then Day 1 of Cycles 2 and beyond (Cycle = 28 days).
- **Ribociclib** tablets should be taken orally in combination with NSAI (non-steroidal aromatase inhibitor) or fulvestrant. Starting dose – 600 mg orally taken once daily for 21 consecutive days followed by 7 days off treatment.
- **Palbociclib** capsules should be taken orally with food in combination with an NSAI or fulvestrant. Starting dose – 125 mg orally taken once daily for 21 consecutive days followed by 7 days off treatment.
- **Abemaciclib** tablets should be taken orally in combination with NSAI or fulvestrant. Starting dose – 150 mg twice daily
- **Letrozole** 2.5 mg or **anastrozole** 1 mg orally should be taken orally daily
- Pre/Peri-menopausal women treated with CDKI plus NSAI or fulvestrant therapy should be treated with luteinizing hormone-releasing hormone (LHRH) agonists according to current clinical practice standards.

Since treatment involves standard of care agents, patients can pursue treatment outside of MD Anderson, under the supervision of the local oncologist. However, clinical documents to confirm administration should be sent for review. Additionally, clinical assessments to confirm response (e.g. staging scans) should be performed at MD Anderson.

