6.2. Evaluation during study

Follow up laboratory assessments should be performed as per standard of care for palbociclib, ribociclib, abemaciclib, and fulvestrant

- Physical examination (including vital signs, weight, performance status)
- Patients will undergo restaging with complete imaging (CT CAP and bone scan) approximately every 3-4 cycles of therapy for the first 12 months and every 3-6 months thereafter until progression.
- Exploratory ctDNA blood draws (Guardant360 StreckTM cell preservation tubes (8-10 mL x 2 per blood draw) will be performed at Cycle 2, Cycle 4 and Cycle 12. These will be banked at MDACC. ctDNA will be drawn on the same date as standard of care labs assessments.
- End of Treatment/Progression ctDNA Blood draw (Guardant360 StreckTM cell preservation tubes (8-10 mL x 2 per blood draw).

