7. MEASUREMENT OF EFFECT

7.1. RECIST Criteria in metastatic disease

Tumor response for patients with measurable lesions should be assessed using RECIST 1.1[32]. Patients with measurable lesions should be assessed using contrast-enhanced CT of the chest, abdomen and/or MRI scan of the chest, abdomen and pelvis approximately (+/- 7 days) every three cycles (cycle length is 28 days), from the date of first dose of fulvestrant until the 30-day follow-up visit. Although progression may be determined by the investigator based upon clinical deterioration, every effort should be made to document progression using radiographic methods. The basis for determination of progression per clinical deterioration should be documented.

Note: It is very important that the same method of radiologic assessment be used throughout the study and that the same lesions are followed.

Response Criteria

Changes in the largest diameter of the tumor lesions and the shortest diameter in the case of malignant lymph nodes should be used in RECIST assessment.

Complete Response (CR): Disappearance of all target lesions. Any pathological lymph nodes (whether target or non-target) must have reduction in short axis to <10 mm.

Partial Response (PR): At least a 30% decrease in the sum of the diameters of target lesions, taking as reference the baseline sum diameters.

Progressive Disease (PD): At least a 20% increase in the sum of the diameters of target lesions, taking as reference the smallest sum on study (this includes the baseline sum if that is the smallest on study). In addition to the relative increase of 20%, the sum must also demonstrate an absolute increase of at least 5 mm. (Note: the appearance of one or more new lesions is also considered progressions).

Stable Disease (SD): Neither sufficient shrinkage to qualify for PR nor sufficient increase to qualify for PD, taking as reference the smallest sum diameters while on study.

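### PFS is censored at the last clinical evaluation or last follow-up, not at the last tumour assessment, so time after the last scan is counted as progression-free

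*Combined protocol and SAP*

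**What the plan says.** Section 9 of the combined protocol and SAP gives the censoring date for PFS twice. The definition of PFS runs from randomisation to death or progression, "or the date of last follow-up if no event has occurred". Two sentences later: "Patients alive and disease-free at the latest clinical evaluation will be censored for PFS at the date of that evaluation". The second sentence speaks of disease-free patients, although everyone enrolled has metastatic disease, so it needs interpreting before it can be applied.

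The passages that determine how far a clinic date can lie from a scan date are these:

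- Section 6.2 (and Appendix 1, note b): restaging scans "approximately every 3-4 cycles of therapy for the first 12 months and every 3-6 months thereafter until progression".
- Section 7.1: for measurable disease, scans "every three cycles (cycle length is 28 days), from the date of first dose of fulvestrant until the 30-day follow-up visit".
- Section 7.1 also says that "progression may be determined by the investigator based upon clinical deterioration", while asking for radiographic documentation wherever possible.
- Section 5.1: "patients can pursue treatment outside of MD Anderson, under the supervision of the local oncologist". The same section and Appendix 1 say that staging scans should be done at MD Anderson.
- Section 5.1 on fulvestrant injections: "on days 1, 15 of Cycle 1 and then Day 1 of Cycles 2 and beyond (Cycle = 28 days". Control patients continue their oral treatment.

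I found no rule for missed scans or for new therapy started before progression.

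**The concern.** Progression in this trial is found mainly by scans. A patient seen locally two months after a clean scan has no imaging evidence for those two months, yet the rule counts them as progression-free. Two things are at stake.

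- **Medians and hazard ratio.** Patients who are no longer scanned but remain in follow-up stay in the risk set with little chance of an event. That lifts the Kaplan-Meier curves and can distort the treatment comparison.
- **Analyst discretion.** Section 9 describes the design as "This is a randomized, open-label, Phase II", with an interim analysis at 42 events. Two differently worded censoring dates leave a choice that could be made after data have been seen.

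Sections 6.2 and 7.1 also disagree on when imaging ends: at progression in one, at the 30-day follow-up visit in the other. Under 7.1, a patient who stops treatment without progression need not be scanned after that visit. Section 5.5 follows all patients, including early stoppers, until a month after therapy for metastatic disease ends. If that includes later lines of therapy, follow-up can outlast scanning.

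**Working it through.** **1. The plan's own figure.** Section 9 gives median PFS of 5 against 9 months, 124 patients, 4-5 per month, 5 months of follow-up, two-sided 5%, 84 expected events, and 81% power in its table.

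- HR = 5/9 = 0.556, ln HR = -0.588.
- Events for 80% power (Schoenfeld): 4 × (1.96 + 0.842)² / 0.588² = 90.9, so 91.
- Exactly 84 events: Φ(√84/2 × 0.588 - 1.96) = Φ(0.73) = 76.8%.
- Events expected with exponential PFS and uniform accrual at 4.5 per month (27.6 months, then 5 more): 62 × (0.872 + 0.718) = 98.6. The range is 96.5-100.8 for 5 down to 4 per month.
- With a maximum of 98 events and the stated interim rules, simulated power is 80.8-81.2%, matching 81%. Expected events averaged over early stopping are 86.0, close to 84.

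The stated power therefore reproduces. It does not involve the censoring rule.

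**2. Rough size of the unscanned interval.** If data cut-off falls at random between scans, the mean time since the last scan is half the interval: 6-8 weeks (1.4-1.8 months) in year 1 and 1.5-3 months later. Four-weekly visits leave on average 2 weeks (about 0.5 month) between last visit and cut-off. The credited unscanned time is thus about 0.9-1.3 months in year 1 and 1.0-2.5 months later.

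**3. Simulation of the two rules on the same data.** Inputs from the plan: 124 patients, medians 5 and 9 months, 5 months of follow-up, the section 6.2 scan intervals, and scans within 7 days of schedule. Assumed: 1:1 allocation, accrual of 4.5 per month, exponential PFS, every visit interval, every rate of stopping scans, and no death or clinical progression between scans unless stated. No interim look is modelled. Each cell gives censoring at last visit / censoring at last scan.

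| Scenario (assumed) | HR | Fulvestrant median, months | Power |
|---|---|---|---|
| A. Four-weekly visits in both arms, complete scanning | 0.556 / 0.557 | 10.8 / 10.4 | 79.0% / 78.6% |
| B. As A, but 3% per month stop scanning and are seen 6 more months | 0.568 / 0.556 | 12.7 / 10.1 | 66.7% / 69.1% |
| C. 2% per month stop scanning and are seen to data cut-off | 0.61 / 0.57 | 13.2 / 10.3 | 61% / 73% |
| D. Fulvestrant 4-weekly, AI 12-weekly; 2% per month stop scanning, 1 more month of follow-up | 0.540 / 0.561 | 10.9 / 10.2 | 77.0% / 71.3% |

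- **A:** unscanned time per censored patient is 1.52 months (AI) and 1.56 (fulvestrant), in line with step 2. The AI median is 6.9 / 6.8 months.
- **B:** the AI median is 7.8 / 6.6 months. With no treatment effect the HR is 1.01 under both rules.
- **C:** patients no longer scanned cannot have an event but stay at risk. They form a larger share of those at risk in the faster-progressing arm, so its apparent hazard falls more and the HR moves toward 1. If 40% of progressions are recognised clinically, power is about 72% / 79%, so the gap narrows from about 12 to 7 points; the amount depends on how soon they are recognised.
- **D:** the HR shift is 1 - 0.540/0.561 = 3.7%. With no treatment effect the HR is 0.97 / 1.00. With the same visit pattern and complete scanning the shift is about 2% (0.974 / 0.996 with no treatment effect). The higher power under last-visit censoring in D reflects that bias, not a gain.

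Censoring at the last scan does not recover events lost when scanning stops, and does not remove the inflation that comes from the scan interval itself (10.4 against a true 9 months in A).

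**The case against.** **A stronger reading that a reader might infer** is that unscanned time is credited unequally and so biases the result toward fulvestrant, because injections bring those patients in every 28 days. The documents do not support this as fact. Section 6.2 and Appendix 1 set one evaluation and imaging schedule for both arms; only the fulvestrant row is arm-specific. Nothing says that an injection visit counts as a clinical evaluation. Section 5.2 cites blood counts at the start of each cycle for palbociclib, which may be given in either arm, so monthly contact is not peculiar to fulvestrant. With equal visits, the unscanned time per censored patient is the same in both arms to within 0.04 months.

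What stands is a risk, from open-label treatment, the injections, and the section 7.1 imaging clock, which starts at a fulvestrant dose that control patients never receive. A large distortion can be constructed: if 3% per month stop scanning and only the fulvestrant arm is followed for 6 further months, type I error reaches 23% against 5%. Nothing in the plan describes that pattern.

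**Other objections.**

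- Clinical progression counts under section 7.1, so a visit without progression is weak evidence rather than none. This stands; it shrinks the effect and must be reflected in the fix.
- The two sentences could be one loosely worded rule, with the second specifying the first. That is possible, but neither reading points to the last scan.
- The power loss needs patients to stop scanning while staying in follow-up, at a rate the documents do not give. This also stands; B and C show a range, not a forecast.

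**Conclusion.** The point holds as a defect in the censoring rule. With complete scanning and equal visits its effect is small: about 1.5 months per censored patient, about 0.4 months on the fulvestrant median, about 0.1 on the AI median, and almost nothing on the hazard ratio. If scanning stops while follow-up continues, both medians are inflated and the hazard ratio is diluted, from 0.57 to 0.61 in the heavier assumed scenario, with power about 12 points lower than under last-scan censoring. That works against finding a benefit.

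A difference between arms is possible but not stated; assumed 4- against 12-weekly visits move the hazard ratio by about 2-4%. A reader should not conclude that the plan favours fulvestrant or that its type I error is compromised. All these sizes rest on assumed visit patterns and scan-stopping rates, and on stopping that is unrelated to progression. The sample size and stated power are unaffected.

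**What to change.** Replace both censoring statements in section 9 with one rule. Patients without documented progression (radiographic, or clinical as section 7.1 allows) or death are censored at the date of their last adequate tumour assessment, or at randomisation if there is none. Define what makes an assessment adequate. Keep censoring at the last clinical evaluation as a named sensitivity analysis.

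Reconcile sections 6.2 and 7.1 on the interval, starting date and end of imaging, so that one schedule applies to both arms and counts from a date that every patient has.

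Cost: a few sentences. Scan dates are needed anyway to date progression. Censored patients contribute slightly less follow-up. There is also an asymmetry to acknowledge: an event-free clinic visit after the last scan is not credited, although clinical progression at the same visit would count as an event. The sensitivity analysis shows whether that matters. Label: cheap improvement.
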